5.1.4.2 Functional blinding

First-dose effects on HR and AV conduction, and lymphocyte count reduction have been identified as potentially unblinding information. Access to this information by the site's staff and sponsor's study team will be restricted. The following measures will be taken to ensure that the efficacy assessments (i.e., EDSS/FS) are done independently and that cardiac safety assessments, and lymphocyte count assessments are performed and reviewed without potential to introduce a bias:

- The primary endpoint (ARR) and the first secondary endpoint (disability accumulation) are based on the evaluations of the EDSS and FS scores, assessed by an efficacy assessor, not involved in any other aspects of patient care and management throughout the study.
- The subject will be instructed not to discuss AEs (other than those required for EDSS assessments), HR, pulmonary function and/or concomitant medications and any other medical event that have the potential of revealing the treatment allocation with the efficacy assessor.
- The principal investigator / treating neurologist and first-dose administrator evaluating cardiac safety assessments must not discuss any issues related to patient care and management unless mandated for reasons of subject safety. On Day 1 and on the first day of re-initiation of study drug when post-dose monitoring is required, significant findings, which in view of the first-dose administrator meet the definition of an AE, have an onset after the study drug intake and are resolved at the time of discharge of the subject, must be recorded directly on the AE page of the separate eCRF by the first-dose administrator / delegate. These AEs, the ECGs interpretation

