reports and BP data collected on these days will not be visible to any of the blinded study personnel at the study site. During the study, all clinical records related to first dose data (e.g., 12-lead ECG printouts, BP results, AEs, etc.) must be filed in a separate medical chart only visible to the first-dose administrator. At the sponsor's level, these events and ECGs and BP data will be entered into a separate eCRF and will only be visible to the site monitor and to the first-dose monitor. The site monitor will not reveal any potentially unblinding information to the rest of the site team or to the sponsor study team and will only discuss any of these data with the first-dose administrator or the first-dose monitor. The first-dose monitor is a role created by the sponsor for medical and scientific review of the BP and 12-lead ECG data assessed during cardiac monitoring after first dosing or after re-initiation. In order to keep the rest of the sponsor's team blinded the first-dose monitor will not reveal any potentially unblinding information to the site team or to the rest of the sponsor study team and will be clearly identified. Her/his access to potentially unblinding information will be documented in the trial master file.

- Results of the total WBC count and total lymphocyte count assessed during the double blind treatment period will not be communicated to the sites, sponsor, and CRO involved in the conduct of the study unless one of the below applies:
 - A total lymphocyte count $< 0.2 \times 10^9/L$ is recorded by the central laboratory. In this event, an alert containing the total lymphocyte count result will be sent to the principal investigator / treating neurologist and the sponsor. FU monitoring must be provided as described in Sections 5.1.12.2 and 7.3.13.
 - A WBC count $> 20 \times 10^9/L$ or a lymphocyte count $> 8.0 \times 10^9/L$ is recorded by the central laboratory. In this event, an alert containing the total WBC or lymphocyte count result (as applicable) will be sent to the principal investigator / treating neurologist and the sponsor.

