7.3.13 Laboratory assessments

7.3.13.1 Type of laboratory

A central laboratory (see central laboratory manual for contact details) will be used for all protocol-mandated laboratory tests, including re-tests due to laboratory abnormalities and laboratory tests performed at unscheduled visits. Central laboratory data will be automatically transferred from the central laboratory database to Actelion's clinical database.

Under specific circumstances (e.g., if the subject lives far from the site and cannot return every 4 weeks (\pm 3 days) for the lymphocyte count assessments), laboratory samples may be collected at a laboratory close to where the subject lives (satellite laboratory), and sent to the central laboratory for analysis. In such a case, the satellite laboratory must be provided with the central laboratory sampling kits, which must be used for blood collection. The blood samples collected locally will be shipped by the local laboratory to the central laboratory for analysis. Such a local laboratory shall be identified as soon as possible, but no later than upon enrollment of the subject in the study.

In exceptional cases (e.g., subject is hospitalized in a different hospital from the study center due to a medical emergency, or missing central laboratory values) local laboratory results (with the corresponding normal ranges) will be entered into the clinical database via dedicated CRF pages.

If a central laboratory sample is lost or cannot be analyzed for whatever reason, the investigator may collect an additional sample as soon as possible for retest analysis, unless a local laboratory sample was collected within the same time-window and these test results are available.

The central laboratory will provide all laboratory results by fax or email to the site with the exception of the results of the total WBC count and total lymphocyte count. The lymphocyte count results obtained during treatment period will be communicated to the site only if one of the below applies:

- A total lymphocyte count $< 0.2 \times 10^9/L$ is recorded by the central laboratory. In this event, an alert containing the total lymphocyte count result will be sent to the principal investigator / treating neurologist and the sponsor [see Section 5.1.12.2].

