8.4.3 Unscheduled visits (any other assessment;U1, U2, U3, etc.)

An unscheduled site visit may be performed at any time during the study (between scheduled visits), as necessary, at the investigator's discretion. The date of the visit and the reason for such visits as well as any data related to study assessments performed at unscheduled visits will be recorded in the eCRF. During such visits, any of the following assessments may be performed at the investigator's discretion:

- EDSS/FS.
- FSIQ-RMS.
- MRI.
- Assessment of concomitant medications.
- Physical examination.
- Body temperature.
- Pulse rate (to be assessed only if no 12-lead ECG is performed at this visit)
- SBP/DBP.
- 12-lead ECGs (e.g., in case concomitant treatment with a QT-prolonging drug with known risk of Torsades de Pointes is needed [see [Appendix 4](#)]).
- Ophthalmological examination (e.g., presence of visual symptoms suggestive of active uveitis [see Section [5.1.12.7](#)]).
- OCT (e.g., presence of visual symptoms suggestive of macular edema or active uveitis [see Section [5.1.12.7](#)]).
- Spirometry.
- Complete laboratory tests including: hematology including lymphocytes, blood chemistry, viral serology, urinalysis, or serum pregnancy test (for WOCBP only).
- Assessment of AEs and SAEs.
- Dermatological examination.
- Assessment of methods of contraception (for WOCBP only).
- Measurement of body weight.
- IRT call – return of study drug blisters and unused medication, and dispensing of new blisters, if appropriate.
- PK – when possible, a PK sample will be collected for all subjects experiencing SAEs. In this event, a sample will preferably be collected pre-dose (trough), as early as possible after SAE onset, and no later than 7 days after the last dose of study drug.

Additional unscheduled spirometry will have to be conducted in the event of respiratory symptoms (e.g., dyspnea) during the course of the study. An inhaled short-acting β 2 agonist (e.g., albuterol/salbutamol) for symptom relief may be administered at the discretion of the investigator. Administration of any short-acting β 2 agonist will be recorded in the eCRF.

If any of the laboratory variables listed in Section 7.3.13.2 needs to be analyzed, this must be done at the Central Laboratory, except in case of emergency; if it has been done at a local laboratory, results must be recorded in the eCRF [see Section 7.3.13].

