12 DATA HANDLING

12.1 Data collection

The investigator/delegate is responsible for ensuring the accuracy, completeness, and timeliness of the data reported. All source documents should be completed in a neat, legible manner to ensure accurate interpretation of the data. Data reported in the eCRF derived from source documents must be consistent with the source documents.

Electronic CRF data will be captured via electronic data capture (using the Rave system provided by Medidata Solutions, Inc., a web-based tool). The investigator and site staff will be trained to enter and edit the data via a secure network, with secure access features

(username, password and identification – an electronic password system). A complete electronic audit trail will be maintained. The investigator/delegate will approve the data (i.e., confirm the accuracy of the data recorded) using an electronic signature (refer to 21 CFR Part 11). In addition to the main eCRF, a separate eCRF will be used to collect data with unblinding potential generated on Day 1 and on the first day of re-initiation of study drug when post-dose monitoring is required. This data will only be visible to the site monitor, the first-dose monitor and to an Independent Data Management Team [see Sections 5.1.4.2 and 10.1.5].

Entries recorded by the subject in the electronic diary (FSIQ-RMS, SF-36v2TM, and WPAI:MS) and the eC-SSRS are considered source data. The site staff will review and ensure completeness and readability (if applicable) of the subject's entries.

Subject screening and enrollment data will be completed for all subjects (i.e., eligible and non-eligible) through the IRT system and eCRF.

For each subject enrolled, regardless of study treatment initiation, a eCRF must be completed and signed by the investigator/delegate. This also applies to those subjects who fail to complete the study. If a subject withdraws from the study, the reason must be noted on the eCRF.

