12.3 Database management and quality control

Electronic CRFs will be used for all subjects. The investigator will have access to the site eCRF data until the database is locked. Thereafter, they will have read-only access. The eCRF must be kept current to reflect subject status at any timepoint during the course of the study.

While entering the data, the investigator/delegate will be instantly alerted to data queries by validated programmed checks. Additional data review will be performed by Actelion on an ongoing basis to look for unexpected patterns in data and study monitoring. If discrepant data are detected, a query specifying the problem and requesting clarification will be issued and visible to the investigator/delegate via the eCRF. All electronic queries visible in the system either require a data correction (when applicable) and a response

from the investigator/delegate to clarify the queried data directly in the eCRF, or simply a data correction in the eCRF. The investigator/delegate must, on request, supply Actelion with any required background data from the study documentation or clinical records. This is particularly important when errors in data transcription are suspected. In the case of health authority queries, it is also necessary to have access to the complete study records, provided that subject confidentiality is protected.

This process will continue until database closure.

Laboratory samples, ECGs, eDiary, SF-36v2TM, FSIQ-RMS, eC-SSRS and WPAI:MS assessments will be processed centrally through their respective central laboratory/provider, and the results will be sent electronically to Actelion. If local laboratory date is obtained as may be required per protocol in certain instances, it must be entered in the eCRF by the site.

After the database has been declared complete and accurate, the database will be closed. Any changes to the database after that time may only be made as described in the appropriate SOP. After database closure, the investigator will receive the eCRF of the subjects of her/his site (including all data changes made) on electronic media or as a paper copy.

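### Section 7.3.13.1 admits local results for missing central values without excluding WBC and lymphocyte counts, leaving a gap in the functional blinding of Section 5.1.4.2

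*Protocol*

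**What the plan says.** Section 5.1.4.2 states the premise: "First-dose effects on HR and AV conduction, and lymphocyte count reduction have been identified as potentially unblinding information". It then sets the rule: "Results of the total WBC count and total lymphocyte count assessed during the double blind treatment period will not be communicated to the sites", nor to the sponsor or the CRO, unless a listed case applies. The list contains three on-treatment alerts (a very low count, a very high count, and a sustained fall from Week 4), a low count at the follow-up visit, and counts taken in the post-treatment observation period. Local testing is not on it. Section 3.7.2 likewise leaves WBC and lymphocyte counts out of the laboratory results that the treating neurologist reviews.

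Section 7.3.13.1 implements the rule by having the central laboratory withhold the two results. The same section names as exceptional cases an admission to another hospital in an emergency, "or missing central laboratory values) local laboratory results (with the corresponding normal ranges) will be entered into the clinical database via dedicated CRF pages", so one of its two examples is simply that a central value is missing. It also provides for an additional sample when a central one is lost, "unless a local laboratory sample was collected within the same time-window and these test results are available".

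On recording, Section 8.4.3 says of unscheduled visits that "if it has been done at a local laboratory, results must be recorded in the eCRF", and Section 12.3 says of local data that "it must be entered in the eCRF by the site". Section 12.1 describes the masked alternative: "a separate eCRF will be used to collect data with unblinding potential generated on Day 1 and on the first day of re-initiation".

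**The concern.** The masking of WBC and lymphocyte counts depends on one mechanism, the central laboratory not sending them. A locally analysed blood count bypasses it, because the report comes back to the site.

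The primary endpoint is at stake. Under Section 7.2.2 the treating neurologist judges whether symptoms are likely to be a relapse, refers the subject for EDSS scoring, and then decides whether the relapse is confirmed. A neurologist who has seen an on-treatment count may have a good idea of the arm when making those judgments. The sponsor's study team, which Section 5.1.4.2 also keeps from the counts, is exposed by the same route.

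**Working it through.** The plan states no figure to reproduce, so the check sets the sections side by side.

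1. **Which tests can be local?** Section 7.3.13.1 does not restrict the local route to particular tests. The hematology panel in Section 7.3.13.2 includes total and differential WBC counts. Nothing takes them out of the local route.

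2. **Is the route confined to emergencies?** Not in Section 7.3.13.1, where a missing central value is a reason of its own. Section 8.4.3, for unscheduled visits, requires central analysis except in an emergency. Section 5.1.12.2 repeats a low lymphocyte count centrally unless the clinical situation demands immediate local testing. The missing-value clause is the outlier.

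3. **Where do the results go?** On dedicated CRF pages (7.3.13.1), recorded in the eCRF (8.4.3) by the site (12.3). The separate eCRF, visible only to the site monitor, the first-dose monitor and an independent data management team, is defined for Day 1 and the first day of re-initiation (12.1). Later local counts fall outside it, and no viewing restriction is stated for the dedicated pages.

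4. **Who reads the report?** Section 7.3.13.1 requires the principal investigator or a delegate to sign every laboratory report within 5 calendar days and to judge the relevance of abnormal values. Under Section 3.7.2 the treating neurologist may be the principal investigator.

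5. **Was a masked alternative available?** Yes. Satellite laboratories may draw blood, but the samples are still analysed centrally (7.3.13.1). A redraw after a lost sample is already foreseen in 7.3.13.1 and 7.3.13.2.

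6. **How informative could a count be?** Section 1.3.2.2 gives Phase 2 mean changes at Week 24 of −65.3% on ponesimod 20 mg and +3.3% on placebo. As an illustration, assume that these means carry over to subjects on DMF, and take a baseline at the lower entry limit of 0.8 × 10⁹/L (Section 4.3, criterion 8):
   - ponesimod: 0.8 × (1 − 0.653) = 0.8 × 0.347 ≈ 0.28
   - placebo: 0.8 × (1 + 0.033) = 0.8 × 1.033 ≈ 0.83

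   A steady 0.28 lies above the 0.2 alert. If it was already reached by Week 4, it would not meet the alert for a fall of more than 50% from Week 4 either. The central laboratory would not release it, whereas a local report would show it.

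**The case against.** The case for leaving the text alone has several parts.

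- **The route is narrow.** Section 7.3.13.1 opens by requiring the central laboratory for all protocol-mandated tests, and local results are for exceptional cases. This stands, and the protocol gives no frequency.
- **The lost-sample clause creates no new exposure.** It applies when a local result already exists, so skipping the redraw shows nobody anything further. This stands. The weight rests on the missing-value clause and on the absence of masking for local results.
- **Exposure is not stated as a fact.** A reader might infer that local counts go into the ordinary eCRF and do reach the neurologist. The text says dedicated CRF pages and does not say who views them, and the laboratory manual, not shown, may add masking. Exposure is possible and unprevented, no more. The blinding section gives an explicit exception list, though, and should not depend on another document to close the gap.
- **One count does not settle the arm.** A reader might infer this from the Phase 2 contrast. Those are group means without spread, from a study of ponesimod against placebo without DMF as an add-on background. DMF itself lowers lymphocytes, and Section 3.4.1 says the effect of adding ponesimod to it has not been studied in humans. A count is suggestive only.
- **Other safeguards remain.** The efficacy assessor is kept from laboratory results (3.7.3), the neurologist may not alter EDSS/FS scores (7.2.2), and confirmation needs a numeric increase (6.1.1). Section 11.3.2.2.2 compares between arms the share of reported symptoms taken as relapses and as confirmed relapses. These limit the possible bias to referral and to the judgment that scores fit the symptoms. The planned comparison can reveal an imbalance but cannot undo it.

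**Conclusion.** The sections contradict each other. WBC and lymphocyte counts are withheld subject to a closed list (5.1.4.2) and kept from the treating neurologist (3.7.2), yet 7.3.13.1 admits local results for a non-emergency reason, has no masking step for them, and departs from the emergency-only condition in 8.4.3. The consequence is an avoidable path by which potentially unblinding data can reach the site, including the person who refers and confirms relapses, and the sponsor team.

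The number of subjects affected cannot be estimated. A reader might take the number of scheduled counts and assume a rate of lost samples. That gives the chance of a missing central value, not the chance that a local count was taken and seen. No sample size, power or alpha figure changes.

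The conclusion assumes that local hematology includes the differential, as the protocol's own panel does, and that no document outside the protocol already masks local counts. The change is worth making because it is cheap and protects a safeguard that the protocol itself treats as necessary.

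**What to change.** 1. In Section 7.3.13.1, adopt the condition already in Section 8.4.3: after randomization and during double-blind treatment, local WBC and differential results are used only in emergencies. A missing or unevaluable central hematology value is handled by a redraw analysed centrally, drawn at a satellite laboratory if distance is the obstacle.
2. Enter any emergency local WBC or differential count on access-restricted eCRF pages, extending the scope of the separate eCRF in Sections 12.1 and 5.1.4.2. Add it to the exception list in 5.1.4.2, and record the subject as potentially unblinded. A restricted form cannot hide a count that the neurologist needed for care, so this record is what allows the exposure to be examined later.

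The cost is protocol wording, one restricted form and an occasional repeat draw of a kind the protocol already foresees. Emergency care is unchanged.

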Based on the interview and examination, the principal investigator / treating neurologist will determine if symptoms are likely to be due to a relapse (i.e., all elements from the relapse definition in Section [6.1.1](#) have been verified, in the absence of another, better explanation of the subject's symptoms). If so, the subject will be referred to the efficacy assessor for an EDSS assessment (Note: at scheduled visits the EDSS assessment planned for this visit will be used). The completed questionnaire [see [Appendix 12](#)] and the outcome of the examination [see [Appendix 13](#)] will be collected in the eCRF.

Step 3: The efficacy assessor will perform the EDSS/FS assessment within 7 days after the onset of new or worsening neurological symptom(s) [see Section [7.2.1](#)]. **Important note:** EDSS and FS assessments will be performed only by the efficacy assessor. The efficacy assessor must not consult prior EDSS/FS scores when performing the current EDSS/FS assessment. In no case will the treating neurologist alter the EDSS/FS score obtained by the efficacy assessor. If the relapse requires treatment with corticosteroids [see Section [5.2.4](#)], treatment should be initiated as early as recommended by local clinical practice. The blinded neurological examination by the efficacy assessor must always be performed prior to the treatment start.

Step 4: The treating neurologist will review the EDSS/FS score obtained by the efficacy assessor and determine presence or absence of qualifying increase in EDSS/FS (i.e., of the magnitude described in Section [6.1.1](#) from a previously clinically stable EDSS/FS score and consistent with the subject's new symptoms). Based on this review, the treating

[figure not shown]
neurologist will decide if the relapse is confirmed or not, according to the protocol definition of confirmed relapse [see Section 6.1.1]. After the occurrence of each confirmed relapse, subjects will be asked to re-consent to continue receiving study treatment [see Section 13.3].

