When applicable, blood samples will be drawn before the morning administration of study medication at Visit 1 (Screening), Visit 2 (Baseline), Visit 4 (Week 2), Visit 5 (Week 4), Visit 6 (Week 12) and every 12 weeks thereafter up to Visit 18 (EOT), and at Visit 20 (FU) and, if applicable, at all corresponding visits in the PTOP (see anticipated total blood volume in [Table 7](#)). Unscheduled laboratory tests may be performed at any time during the study (Visits U1, U2, U3, etc.).

Additional lymphocyte count measurements will be performed every 4 weeks (± 3 days) up to Week 24.

During the pre-randomization period, hematology and clinical chemistry laboratory assessments at Visit 1 (Screening) must be performed a minimum of 21 days before the laboratory assessment at Visit 2 (Baseline).

If a laboratory sample cannot be evaluated (e.g., is lost or deteriorated), an additional sample may need to be taken if deemed necessary by the investigator.

Hematology

- RBC count
- Total and differential WBC counts (basophils, eosinophils, lymphocytes, monocytes, neutrophils, band forms)
- Platelet count
- Hb
- Hematocrit

Clinical chemistry

- Glucose
- ALT, AST, alkaline phosphatase (AP), total bilirubin, lactate dehydrogenase
- INR
- Creatinine
- Calculated creatinine clearance (Cockroft-Gault)
- Urea
- Uric acid
- Total cholesterol
- Triglycerides
- Sodium, potassium, chloride, calcium
- Total protein, albumin
- C-reactive protein

Virus serology

- Hepatitis B surface antigen, Hepatitis C antibodies, HIV1 and HIV2 antibodies, varicella-zoster virus antibodies at Visit 1 (Screening).

JCV serology testing

- JCV antibodies at Visit 2 (Baseline) and every 48 weeks up to Visit 18 (EOT), and, if applicable, at all corresponding visits in the PTOP. Aggregate data from this analysis will be reviewed by the IDMC and the sponsor, but will not be communicated to the sites until database closure unless deemed necessary for safety reasons (i.e., signs or symptoms raising suspicion of PML). In case of screening failure, the sample collected at Visit 2 (Baseline) will not be analyzed.

Additional analyses in the event of infections

- A serum sample will be taken at Visit 2 (Baseline) to be stored at the central laboratory for potential retrospective analyses of viral serology titers in the event of infections (e.g., suspected opportunistic infection) during the study.

Additional analyses in the event of a vaccination with non-live vaccines

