10.4 Study safety monitoring

Clinical study safety information (AEs, SAEs, laboratory values, ECGs, vital signs, and project-specific labs/examinations as required) is monitored and reviewed on a continuous basis by the Actelion clinical team (in charge of ensuring subjects' safety as

well as data quality) by periodically monitoring clinical study activities from protocol conception to database closure. In addition, an IDMC is monitoring safety data [see Section 3.8.1].

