Hematocrit (L/L)	< 0.28 (female) < 0.32 (male)	< 0.20	> 0.55 (female) > 0.60 (male)	> 0.65
Platelet count (10^9 /L)	< 75	< 50	> 600	> 999
RBC count (10^{12} /L)	ND	ND	ND	ND
WBC count (10^9 /L)	NA	< 1.9	> 20.0 ALERT: > 20.0	> 100.0
Lymphocyte (10^9 /L)	ND	< 0.2 ALERT: < 0.2 Decrease of > 50 % from the value of total lymphocyte count recorded at Visit 5 (Week 4) associated with a total lymphocyte count < 0.5×10^9/L recorded at two consecutive visits after Visit 5 (Week 4)	> 4.0	≥ 8
Neutrophils (10^9 /L)	< 1.5	< 1.0	ND	ND

Parameter (SI unit)	LL	LLL	HH	HHH
Eosinophils (10^9 /L)	ND	ND	> 5.0	ND
Monocytes (10^9 /L)	ND	ND	ND	ND
Basophils (10^9 /L)	ND	ND	ND	ND
Polymorphonuclear leucocyte/Band cells (%)	ND	ND	> 90%	> 95%
AST (U/L)*	ND	ND	≥ 3 ULN ALERT: ≥ 3 ULN	≥ 5 ULN ALERT: ≥ 5 ULN ≥ 8 ULN
ALT (U/L)*	ND	ND	≥ 3 ULN ALERT: ≥ 3 ULN	≥ 5 ULN ALERT: ≥ 5 ULN ≥ 8 ULN
Total bilirubin (umol/L)	ND	ND	≥ 2 ULN ALERT: ≥ 2 ULN combined with ALT or AST ≥ 3 ULN	≥ 5 ULN
Alkaline Phosphatase (U/L)	ND	ND	> 2.5 ULN	> 5 ULN
INR*	ND	ND	> 1.5 ULN or > 1.5 times above baseline if on anticoagulation ALERT: > 1.5 combined with ALT or AST ≥ 3 ULN	> 2.5 ULN or > 2.5 times above baseline if on anticoagulation
Lactate dehydrogenase	ND	ND	ND	ND
Creatinine (umol/L)*	ND	ND	>1.5 ULN or >1.5 x baseline	> 3 ULN or >3 x baseline
Creatinine clearance (mL/min)	< 60	< 30	ND	ND
Urea (mmol/L)	ND	ND	> 2.5 ULN	> 5 ULN

Confidential

Parameter (SI unit)	LL	LLL	HH	HHH
Albumin (g/L)	< 30	< 20	ND	ND
Protein total (g/L)	ND	ND	ND	ND
C-reactive protein (mg/L)	ND	ND	ND	ND
Glucose (mmol/L)	< 3.0	< 2.2	> 8.9	> 13.9
Potassium (mmol/L)	< 3.2	< 3.0	> 5.5	> 6.0
Sodium (mmol/L)	ND	< 130	> 150	> 155
Calcium (mmol/L)	< 2.0	< 1.75	> 2.9	> 3.1
Chloride (mmol/L)	ND	ND	ND	ND
Triglyceride (mmol/L)	ND	ND	> 3.42	> 11.4
Cholesterol (mmol/L)	ND	ND	> 7.75	> 12.92
Serum pregnancy test	ND	ND	ND	Positive ALERT: Positive

* HH and HHH based on CTCAE 2010 v4.03 [[CTCAE 2010](#)]. An ALERT will be sent when INR \geq 1.5 based on the guidance for monitoring liver test abnormalities from FDA [[FDA 2009b](#)]

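### The functional-blinding mask covers only total WBC and total lymphocyte count; it should also cover the white-cell differential percentages, from which the lymphocyte effect could be read or back-calculated

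*Protocol*

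**What the plan says.** Section 5.1.4.2 (Functional blinding) names lymphocyte count reduction, with first-dose cardiac effects, as information that could reveal the arm, and says that access by site staff and the sponsor's study team will be restricted. The rule that follows concerns two results: "Results of the total WBC count and total lymphocyte count assessed during the double blind treatment period will not be communicated to the sites", apart from listed alerts.

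Section 7.3.13.1 repeats the two-item mask as an exception to a general rule. The central laboratory provides "all laboratory results by fax or email to the site with the exception of the results of the total WBC count and total lymphocyte count". Details of reporting are left, in that same section, to the laboratory manual.

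The hematology panel in Section 7.3.13.2 is wider than the mask: "Total and differential WBC counts (basophils, eosinophils, lymphocytes, monocytes, neutrophils, band forms". Appendix 6 lists neutrophils in 10^9/L and, as a separate row in percent, "Polymorphonuclear leucocyte/Band cells". Table 6 (Section 5.1.12.6) includes eosinophilia above 5% in a liver criterion.

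Under Section 3.7.2 the treating neurologist reviews routine laboratory results other than WBC and lymphocyte counts. Under Section 7.2.2 the principal investigator or treating neurologist judges whether symptoms are likely to be a relapse and refers the subject for EDSS scoring. At Step 4 the treating "neurologist will decide if the relapse is confirmed or not".

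**The concern.** The mask is a closed list of two totals, and everything outside the list goes to the site. Lymphocyte % is not a total lymphocyte count, and neutrophil % is not a total WBC count, so neither is withheld by the wording. Section 1.3 says ponesimod does not reduce neutrophils or monocytes. A large fall in lymphocytes therefore moves every differential percentage in a predictable direction. The site also holds the subject's pre-treatment counts, because inclusion criterion 8 depends on the Visit 1 and Visit 2 lymphocyte values.

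What is at stake is the primary endpoint. The efficacy assessor is kept from laboratory results (Section 3.7.3), but the person who may receive the differential decides which symptoms count as a suspected relapse and whether a scored event is confirmed. A belief about the arm at those steps could shift the relapse count, and it could not be undone in the analysis.

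**Working it through.** The plan states no figure on this point, so there is none to reproduce. The check is whether the masked count can be derived from what the rule leaves unmasked.

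**Inputs from the protocol.** Mean lymphocyte change at Week 24 in the Phase 2 dose-finding study: -65.3% on 20 mg and +3.3% on placebo (Section 1.3.2.2). Neutrophils and monocytes are not reduced (Section 1.3).

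**Assumed inputs, not in the protocol (10^9/L).** Baseline lymphocytes 0.8 to 2.0; neutrophils 2.7 to 6.0; monocytes 0.3 to 0.7; eosinophils 0.1 to 0.3; basophils 0.02 to 0.08. All non-lymphocyte cells are held unchanged. Middle case: lymphocytes 1.4, neutrophils 4.0, monocytes 0.5, eosinophils 0.2, basophils 0.05, so the non-lymphocyte cells sum to 4.75.

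**Middle case, true values.**
- Placebo: lymphocytes 1.4 x 1.033 = 1.446; WBC 1.446 + 4.75 = 6.20; lymphocyte share 23.3%; neutrophils 64.6%.
- Ponesimod: lymphocytes 1.4 x 0.347 = 0.486; WBC 0.486 + 4.75 = 5.24; lymphocyte share 9.3%; neutrophils 76.4%.

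**Route A: percentages only.** Lymphocyte % = 100 minus the sum of the other percentages. No total is needed, and the result matches the true share to about 0.1 point. Over the assumed grid the share is 10.5% to 39.8% on placebo and 3.8% to 18.2% on ponesimod. These ranges overlap between subjects. For the same starting counts, however, the ponesimod share is well under half the placebo share (3.8/10.5 = 0.36 and 18.2/39.8 = 0.46 at the two ends).

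**Route B: absolute neutrophils plus neutrophil %.** WBC = absolute neutrophils / neutrophil fraction; lymphocytes = WBC minus the other absolute counts.
- Ponesimod, one decimal: 4.0/0.764 = 5.236; 5.236 - 4.75 = 0.486 (true 0.486).
- Placebo, one decimal: 4.0/0.646 = 6.192; 6.192 - 4.75 = 1.442 (true 1.446).
- Whole-number percentages: 4.0/0.76 - 4.75 = 0.513 and 4.0/0.65 - 4.75 = 1.404.

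Over the grid the error is at most about 0.005 with one decimal and about 0.06 with whole numbers. The difference between arms in the middle case is 1.446 - 0.486 = 0.960.

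**Route C: absolute counts of the other cells only.** Total WBC is unknown and no equation contains lymphocytes. The count cannot be derived.

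The exposure therefore depends on one fact that the protocol does not fix: whether any differential percentage appears on the site report.

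**The case against.** **Report format.** The laboratory manual, which is not at hand, may already restrict site reports to absolute counts. Appendix 6 does not prove that percentages reach sites: it also lists the masked WBC and lymphocyte rows, and its thresholds serve sponsor reporting too. The Table 6 eosinophil item applies only alongside raised transaminases. Section 3.7.2 excludes WBC and lymphocyte counts without the word total, which could be read to cover the differential. This stands as far as it goes: the protocol does not show that the route is open. But the two sections that set the mask say total, and the general rule sends everything else. Where other results were to be withheld, the protocol says so, as for JCV serology (Section 7.3.13.2) and lymphocyte subsets (Sections 3.6.1 and 7.7.2.2).

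**Endpoint safeguards.** Confirmation needs a qualifying EDSS/FS increase (Section 6.1.1) from an assessor shielded from laboratory data, and the neurologist may not alter the scores. Detection uses structured questionnaires and scheduled calls, and EDSS is scored every 12 weeks whether or not there is a referral. Section 11.3.2.2.2 compares between arms the proportion of reported symptoms taken as relapses and as confirmed relapses; Section 11.3.2.4 adds an analysis of all relapses. These limit the exposure. They do not remove it: an imbalance in referral could reflect bias or drug effect, and the comparison cannot separate the two.

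**Sponsor access.** A reader might infer a contradiction from three statements: the counts "will not be communicated to the sites, sponsor, and CRO involved in the conduct of the study"; "Central laboratory data will be automatically transferred from the central laboratory database" to the sponsor's clinical database; and safety information, laboratory values included, "is monitored and reviewed on a continuous basis by the Actelion clinical team". The protocol does not support that reading. Section 5.1.4.2 already restricts the sponsor's study team, and automatic transfer describes where data go, not who may view them. A cross-reference would be useful; there is no breach to report.

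**Lymphocyte effect.** The figures come from Phase 2 without DMF. Section 3.4.1 says the effect of the combination has not been studied in humans, and that DMF itself lowers counts with a nadir after one year. Separation between arms could be smaller than in the example.

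**Conclusion.** The mask is narrower than the risk that the protocol itself identifies. Taken literally, it allows differential percentages to reach the person who decides relapse referral and confirmation. If any percentage is on the report, the lymphocyte share or the masked count can be obtained; if only absolute counts of the other cells are reported, it cannot. That conclusion is arithmetic and does not depend on the assumed cell levels. The size of the shift in the example does depend on them, and on the Phase 2 effect carrying over to add-on use.

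A reader might go further and infer that treating neurologists are in fact unblinded, or that the annualized relapse rate ratio is biased by some stated amount. The protocol supports neither. The report format is not given, nothing shows that neurologists would infer the arm or act on it, and no bias in the relapse rate can be computed. This is a worthwhile, inexpensive tightening of the blind, not a defect that invalidates the primary analysis.

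**What to change.** Amend Sections 5.1.4.2 and 7.3.13.1 so that, from randomization until the FU visit:

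- the mask also covers every white-cell differential percentage, including lymphocyte % and the polymorphonuclear/band % row of Appendix 6;
- the remaining white cells go to sites as absolute counts only;
- the central laboratory issues the existing Table 6 eosinophil criterion as a yes/no flag, with the criterion itself unchanged;
- all existing WBC and lymphocyte safety alerts stay as they are.

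Add one sentence to each of Sections 7.3.13.1 and 10.4 saying that transferred WBC, lymphocyte and differential data fall under the access restriction already given in Section 5.1.4.2. Align the laboratory manual with this wording; if it already reports absolute counts only, the amendment simply records current practice.

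The cost is a report configuration at the central laboratory and a short protocol clarification. The downside is that sites lose percentage values during treatment; they keep absolute neutrophils and every alert. Sample size, alpha and the analysis model are unaffected.
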